3.7.4 Surgical Time

Time of skin incision and last skin suture will be documented to determine surgical time. It will be presented in minutes.

3.7.5 Surgical Technique

Qualified Orthopaedic surgeons will perform the surgeries and the surgical technique shall be as below:

The choice of ante grade or retrograde nailing can also be influenced by a number of factors including the patient's body habitus, the condition of the soft tissues, and concerns regarding positioning of the patient during anesthesia.

Ante grade Technique

This technique will be preferred for fractures of the proximal or middle third of the femur shaft as the centered starting point helps to ensure that the nail will be centered within the distal fracture fragment. Antegrade nailing will be performed with the patient in the lateral position.

Open reduction of the fracture will be used. The length of the skin incision will depend primarily on the duration since the injury, the more the time the longer the incision as wider dissections are required to release the use a periosteal elevator to longitudinally separate the muscle fibers of the vastus lateralis down to the fracture site. Free up the callus and soft tissues with aid of periosteal elevators and osteotomes until each fracture fragment is free. Surgeon will preserve immature callus to fill the dead space. Once fragments are free, hand reaming will be performed through the fracture site until the full length of the isthmus had been reamed. Any bone retrieved from the flutes of the reamer will be saved for placement in the fracture site at the end of the procedure. Then the surgeon with aid of assistants and manual maneuvers will reduce the fracture ensuring

to line up the linea aspera on both sides of the fracture to accomplish rotational alignment.

Accurate rotational alignment of the fracture site is an advantage of open reduction over closed reduction. Reduction will be held by bone holding clamps.

The proximal incision will be made and the proximal aspect of the femur was entered with use of a curved awl positioned at the tip of the greater trochanter or piriformis fossa between the posterior and middle thirds of the femur. Hand reamers will then be used to ream the segment of bone between the osseous entrance and the femur shaft. The reaming will also be used to determine the proper nail diameter, which is 2 mm less than the diameter of the reamer that will elicits “chatter” for a distance of approximately 6 cm.

The target arm will then be attached to the nail, and the longitudinal positions of the proximal and distal interlocking screws noted. The target arm will then be removed and the nail inserted, with rotation allowed during placement of the nail. After the nail is inserted, the target arm will be reattached to guide the placement of the interlocking screws. Two, three or four interlocking screws will be used. A window will be drilled in the near cortex at the position indicated by the target arm, and a specially designed cannulated slot finder will be placed through this cortical window into the slot of the nail. The hole in the far cortex will then be drilled through the cannulated slot finder, the length of the screw will be measured, and the interlocking screw will be placed. The proximal interlocking screws will be placed from lateral to medial or from anterior to posterior, with the direction depending on how the nail will be rotated during insertion, as the two orientations provide equal stability.

Retrograde Technique

This technique will be preferred for fractures of the distal third of the femur. Nailing will be performed with the patient in the supine position. As in the antegrade technique, the fracture site will be opened to allow for reduction as well as reaming through the fracture site. After the knee incision will be made, the femoral canal will be opened distally with use of an awl, and hand reaming will be performed. The nail will be inserted in a retrograde direction and the target arm will be used to place the interlocking screws with use of a technique similar to that described for antegrade technique.

Electro cautery will be used for all patients undergoing ORIF.

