1.1 Background

Major orthopaedic procedures are often associated with major blood loss.(1, 2) Open Reduction and Internal Fixation (ORIF) of femoral shaft fractures is one of major orthopaedic procedures associated with major perioperative blood loss estimated at 1500mls in a developing world operating theatre.(3)

Worldwide major blood losses cause hemodynamic instability and severe anaemia, hence a need for allogeneic blood transfusions that are associated with a number of complications such as (e.g., mismatched transfusion, allergic reactions, transmission of infections, and acute lung injury).(4-6) Furthermore, allogeneic transfusions are also associated with increasing costs such as prolonged hospital stay and the cost of processing, handling, administration of blood products.

Amount of perioperative blood loss during major orthopaedic procedures can be multifactorial with patient and institutional factors. Patient factors do include but not limited, inability to cauterize or coagulate bony surfaces resulting in uncontrollable hemorrhage and increased fibrinolysis as a result of surgical stress. (2, 7) On the other hand institutional factors include availability of electro cautery and fluoroscopy guided intramedullary fracture fixation are believed to reduce intraoperative blood loss.(3)

In the developed and under developed world the need to minimize perioperative blood loss during orthopaedic procedures has been a focus of multiple strategies addressing both patient and institutional factors. (e.g. Hypotensive epidural anesthesia (HEA), Platelet rich plasmapheresis, Acute normovolemic hemodilution (ANH), Cell salvage (scavenging), Anti-fibrinolytics, Fibrin sealants) (1, 8, 9)

Tranexemic acid (TXA) has been used to achieve hemostasis in a number of orthopaedic and non orthopaedic procedures. This is because TXA is an antifibrinolytic agent, a synthetic lysine product that competitively inhibits plasminogen activation to plasmin, and at much higher concentrations, a noncompetitive inhibitor of plasmin, i.e., actions similar to aminocaproic acid. This action prevents dissolution of the fibrin clots stabilizing the clots at the surgical site hence

achieving and maintaining hemostasis.(10-12). TXA has a wide therapeutic window and despite theoretical risk of thromboembolic events has been found to be safe for use in major orthopaedic procedures.(1, 12, 13)

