3.1 Study design

This will be an open label single arm trial involving adult patients undergoing open intramedullary femoral shaft nail fixation at Mulago National Referral Hospital.

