Cross matching done before surgery. Intraoperatively, excessive blood loss is prevented, however not always by use of intravenous Tranexemic acid, tourniquet, diathermy, intraoperative hypotension techniques, and occasionally topical / intramuscular adrenaline concoctions. Blood loss intraoperatively is estimated by anaesthesiologist and surgeon who use visual estimation assessing amount of bleeding at surgical site, blood volume in suction drain containers, soaking of the surgical mops, patient's vitals, level of consciousness and mucous membrane pallor. Intraoperatively blood transfusions are sanctioned by anaesthesiologist depending on visual estimation of blood loss, and patient's hemodynamic stability. Postoperatively patients receive intravenous fluids antibiotics, analgesia and are mobilized in and out of bed 12hours. Patients who are clinically aneamic and hemodynamically unstable have a complete blood count done and transfusions sanctioned by attending physician if necessary. DVT investigation and prophylaxis are not routinely done on patients post operatively however at the discretion of the primary surgeon and attending physician for patients at risk this is done.

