3.6 Sample size estimation

3.6.1 Sampling Procedure

Comparison of Two Means (Minn M. Soe and Kevin M. Sullivan, Emory University)

$$n = \frac{(Z_1 + Z_2)^2}{(u_1 - u_2)^2} 2(S)^2$$

$$(u_1 - u_2)^2$$

n = Sample size in each group

Z₁ = 1.96 for 95% confidence level

Z₂ = 0.84 for 80% power

S = Standard Deviation of Outcome in Control Group

u₂ - u₁ = minimum meaningful difference between means

In study done in Mulago by Kajja et al estimated blood loss in 93 patient who underwent open femur shaft fracture intramedullary nailing estimated 72 hours postoperative mean total blood loss at 3.31g/dl, (SD 1.56).

Tranexemic Acid is expected to give 30% reduction in Blood Loss

i.e. $u_1 - u_2 = 0.3$

u₁

$$\underline{3.31 - u_2} = 0.3$$

3.31

$$u_1 - u_2 = 0.993$$

$$n = (1.96 + 0.84)^2 2 \times 1.56^2$$

$$0.993^2$$

$$= 38.7$$

[figure not shown]
$$n = 39$$

$$\text{Adjust for non-response} = 39 / 0.9$$

$$= 43.3 = 43$$

$$N = 43$$

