3.12 Statistical analysis

Data will then be exported into a SPSS version 19 system which will be used for analysis. We will summarise the study population. We will use descriptive statistics such as means (standard deviations) or median and interquartile range (IQR) for continuous variables and proportions for categorized variables. We will also conduct appropriate statistical tests such as chi square or Fischer's test for categorical variables and a one sample independent T-test or wilcoxon sum rank test for continuous variables.

Objective 1: *To determine the effectiveness of pre-operative intravenous Tranexemic acid 15mg/kg on reduction of perioperative blood loss as estimated by difference in 72 hour postoperative and 2 hour preoperative Hemoglobin concentration in patients undergoing open intramedullary nailfixation offemoral shaftfractures in Mulago National Referral Hospital.*

We will assess for the hypothesis that TXA reduces perioperative blood loss by at least 30% using one sample independent T-test

Objective 2: *To determine effectiveness of pre-operative intravenous Tranexemic acid 15mg/kg on reduction of transfusion rates by 30% inpatients undergoing open intramedullary nail fixation offemoral shaftfractures in Mulago National Referral Hospital.*

We will conduct univariate analysis and adjust for effect modification and confounding.

Objective 3: *To determine the safety of pre-operative intravenous Tranexemic acid 15mg/kg in patients undergoing open intramedullary nailfixation offemoral shaftfractures in Mulago National Referral Hospital.*

We will assess for safety using descriptive statistics showing proportions of adverse events in the study group.

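### A mean loss below the historical 3.31 g/dl cannot be credited to tranexamic acid alone: cautery is universal in the trial, and neither cautery use nor case mix is known for the comparison cohort

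*Combined protocol and SAP*

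**What the plan says.** Section 3.1: "This will be an open label single arm trial". There is no concurrent control.

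The comparator comes from an earlier study at the same hospital, described in section 3.6.1 as "93 patient who underwent open femur shaft fracture intramedullary nailing", which "estimated 72 hours postoperative mean total blood loss at 3.31g/dl, (SD 1.56"). Section 1.4 builds the hypothesis on that 3.31 g/dl. Section 3.12, Objective 1, then says: "We will assess for the hypothesis that TXA reduces perioperative blood loss by at least 30% using one sample independent T-test".

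On cautery, section 3.7.5 says "Electro cautery will be used for all patients undergoing ORIF". Section 1.1, citing reference 3 (the paper of the same cohort), says that "availability of electro cautery and fluoroscopy guided intramedullary fracture fixation are believed to reduce intraoperative blood loss". Section 3.2, on routine practice at the site, says "excessive blood loss is prevented, however not always by use of intravenous Tranexemic acid, tourniquet, diathermy", and goes on to list hypotensive technique and adrenaline.

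Sections 3.5.1 and 3.5.2 limit entry to adults with isolated closed fractures no more than one month old. Repeat surgery, pathological fracture, bleeding disorders and anticoagulant use are among the exclusions.

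Section 3.12 mentions adjustment only under Objective 2. Cautery is neither a study variable (3.8.1) nor an item on the data sheet (Appendix II). The only limitation in section 3.13 is the shared theatre.

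**The concern.** The primary objective is worded causally: the drug reduces blood loss. The only evidence for it will be the gap between the trial mean and a historical mean. Anything else that differs between the two groups and affects bleeding is part of that gap.

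The protocol names one such factor itself. It regards cautery as lowering blood loss, gives it to every trial patient, and does not say how often the cohort had it. Because every trial patient receives cautery, no adjustment within the trial can isolate its effect.

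Case mix raises the same difficulty. Section 3.7.5 says that a longer time since injury means a longer incision and wider dissection, so the one-month limit could plausibly affect blood loss. The protocol does not show that the cohort was restricted in the same way.

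Section 1.3 offers the findings to hospitals and the Ministry of Health as a basis for guidelines. A difference in technique or case mix could then be adopted as a drug effect.

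**Working it through.** **Inputs from the documents.** Historical mean 3.31 g/dl, SD 1.56, 93 patients, expected reduction 30%, z-values 1.96 and 0.84 (all section 3.6.1). Reference value 3.31 (section 1.4). One-sample t-test (section 3.12).

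**Inputs the documents do not give.** The cohort's cautery rate, the size of any cautery effect, the cohort's eligibility criteria, and the reference value of the one-sample test. The shifts below are therefore assumptions shown over a range.

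**Reproducing the plan's figure.** Difference = 0.30 × 3.31 = 0.993 g/dl. n = (1.96 + 0.84)² × 2 × 1.56² / 0.993² = 38.7, rounded to 39; 39/0.9 = 43.3, given as 43. The stated figures reproduce. The formula is for two groups, with n per group, although the design has one.

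**What the test treats as significant.** With n = 39, SE = 1.56/√39 = 0.250 g/dl. The two-sided 5% critical value of t on 38 df is 2.024, so an observed mean 2.024 × 0.250 = 0.506 g/dl below 3.31 is significant. That is 0.506/3.31 = 15%.

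**Non-drug shift with no drug effect, test against 3.31.** Let the shift be f × 3.31. The chance of a significant result in the drug's favour is the upper-tail probability beyond 2.024 of a noncentral t on 38 df, with noncentrality f × 3.31/0.250.

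| Assumed non-drug reduction f | g/dl | Chance of a false finding of benefit |
|---|---|---|
| 0% | 0 | 2.5% |
| 5% | 0.17 | 9% |
| 10% | 0.33 | 25% |
| 15% | 0.50 | 49% |
| 20% | 0.66 | 73% |

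With n = 43 the last four become 10%, 27%, 53% and 78%.

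**What could produce such shifts through cautery alone.** If cautery lowers loss by a fraction r and a proportion p of the cohort had it, the apparent reduction is r(1 − p)/(1 − rp). For r = 20% and p = 0%, 50% or 80%, this is 20%, 11% or 5%, with false-benefit rates of 73%, 30% or 9%. For r = 10% the rates are 25%, 10% and 5%. If p = 100%, the shift is zero.

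**The other reading of section 3.12.** The phrase about a reduction of at least 30% could mean a test against 3.31 − 0.993 = 2.317 g/dl. With no drug effect and a 20% non-drug shift, the true mean is 2.648. The chance of a significant result below 2.317 is then about 0.06%, and it is lower for smaller shifts.

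**Tipping point, as an example.** If the trial observed exactly the planned 0.993 g/dl reduction (n = 39, SD 1.56, reference 3.31), a non-drug difference of 0.993 − 0.506 = 0.487 g/dl, or 15% of 3.31, would be enough to remove significance. This treats 3.31 as known. Allowing for the cohort's own sampling error, the SE is 1.56 × √(1/39 + 1/93) = 0.298 rather than 0.250, so a smaller difference would suffice.

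**The case against.** The strongest reply is that the cautery contrast is inferred. No section gives the cohort's cautery use. Section 1.1 says only that availability is believed to help, and section 3.2 describes routine practice at the time of writing, not the cohort's. If the whole cohort had cautery, this source of bias is zero. That stands, and it is why the figures above are only illustrations.

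A reader might infer that the trial's eligibility is narrower than the cohort's, or its surgeons more experienced. The documents do not support either: section 3.6.1 describes the cohort in one clause and gives neither its criteria nor its surgeons. What can be said is that the trial's restrictions are not shown to match.

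A reader might also infer that the bias favours the drug. That holds for the cautery pathway only if the cohort used cautery less often. The same sentence in section 3.2 lists tranexamic acid itself, tourniquet and other measures as sometimes used. If the cohort had these more often than trial patients will, 3.31 is already lowered and the bias runs towards no effect.

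Finally, the single-arm design is openly declared, and standardising cautery within the trial is reasonable. Both points stand. The sentence on cautery is not a defect in itself; the defect is the causal claim drawn from an uncontrolled comparison. Uncertainty about the size and direction of the imbalance does not rescue that claim.

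**Conclusion.** The point holds as a limit on attribution: a mean below 3.31 g/dl cannot be credited to tranexamic acid alone. It rests on three things in the documents. The comparison is with a historical mean. A factor the protocol itself calls protective is made universal. Nothing in the primary analysis or the stated limitations deals with it.

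The net size and direction of bias are unknown. The rates of about 9%, 25% and 73% for shifts of 5%, 10% and 20% assume no drug effect, n = 39, SD 1.56 and a two-sided 5% test against 3.31. They are not estimates of this trial's error rate; the highest needs, for example, a 20% cautery effect and no cautery in the cohort, and the documents give neither. If section 3.12 means a test against about 2.32 g/dl, the rates fall to 0.06% or less over the same shifts. The attribution problem remains, because that value comes from the same cohort.

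This should be fixed. It changes what the trial may conclude, but it does not require a different design.

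**What to change.** 1. Restate the hypothesis (1.4), the primary objective (1.6.2.1) and the Objective 1 conclusion (3.12) as a comparison of mean loss in tranexamic-acid-treated patients under current technique with the historical mean. State the reference value of the test. Say that a difference is not attributable to the drug alone, and add this to section 3.13.
2. Pre-specify a tipping-point table showing how large a non-drug difference (cautery, case mix) would remove the conclusion, with the cohort's sampling error included.
3. Only if patient-level records of the earlier cohort can be obtained, add a comparison with historical patients who had cautery and meet section 3.5. The documents do not show that such records exist, and the subset would be smaller and its mean less precise.

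Items 1 and 2 need no new patients and no outside data. Their cost is a more modest claim and a small amount of extra analysis. A randomised control is not proposed: by the plan's own formula it needs 39 evaluable patients per arm (78 in total), and splitting the present number into arms of 19 to 21 gives only about 50% to 54% power for 0.993 g/dl.

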3.7.6 Blood use in the perioperative period

The decision to transfuse patients in the intraoperative period will be taken by the anaesthesiologist in concert with the primary surgeon, Basing on:

- Visual assessment of the extent of soaking of the surgical mops with blood.
- Extent of pallor of the finger nail beds, palms and mucous membranes.
- Patient with features of severe hemodynamic instability, tachycardia, hypotension, dizziness etc.
- Post op hemoglobin results of severe anaemia ($\leq 6\text{g/dl}$)

The decision to transfuse patients in the postoperative period will be taken by the primary surgeon or the residents on the wards basing on:

- Patient with features of severe hemodynamic instability, tachycardia, hypotension, dizziness, palpitations etc.
- Extent of pallor of the finger nail beds, palms and mucous membranes.
- Post op hemoglobin results of severe anaemia ($\leq 6\text{g/dl}$)

Intraoperative and postoperative transfusion guidelines shall be availed to the teams to guide on when to transfuse patients to reduce on bias.

Whole blood and packed red blood cell units will be used. 450mls of whole blood and 200mls of packed red blood cells will be estimated to be equivalent to 1g/dl rise in hemoglobin level.

3.7.7 Post-operative care

Patients in the immediate post-operative period will be monitored by the nurses on their primary wards noting vitals (Blood Pressure, Pulse Rate, Respiratory Rates and observe blood soiling of the surgical site dressing). Adequate analgesia will be given to the patients and mobilization in or out of bed will be instituted 12 hours following surgery with guidance of the physiotherapist as per patient tolerability.

Principal investigator together with the surgeons and residents on the primary wards will clinically review the patients daily as part of routine post-operative follow-up with emphasis on identifying and addressing post-operative complications such as thromboembolic phenomena e.g. DVT. Patients with features of thromboembolic phenomena or develop other Serious Adverse

Events will be investigated thoroughly with blood work up PT-INR, aPTT and Doppler Studies for the lower limbs. They will receive treatment as per guidance of qualified physician.

Serious Adverse Events (SAE) shall be reported within 24hours of occurrence to Department Of Orthopaedics, SOMREC, and National Drug Authority (NDA) using National SAE reporting tools.

Patients shall be followed up for a period of 2 weeks post operatively.

3.7.8 Total blood loss

Total blood loss due to the surgical procedure will be represented by total hemoglobin loss in the perioperative period.

Pre-operative hemoglobin (Pre-opHb) will be taken off 2 hours prior to surgery. Post-operative (Post-opHb) hemoglobin will be done 72 hours after surgery, it will be assumed hemodynamic stability is restored at that time.

Total Blood Loss = Pre-opHb – (Post-opHb + Blood Units g/dl)

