NDA	- NATIONAL DRUG AUTHORITY
SOMREC	- SCHOOL OF MEDICINE RESEARCH AND ETHICS COMMITTEE
TXA	- TRANEXEMIC ACID
UBTS	- UGANDA BLOOD TRANSFUSION SERVICES

ABSTRACT

Background: Major Perioperative blood loss is one of the complications of open femoral shaft fracture intramedullary nailing surgery with average blood loss estimated at 1500mls. There is need for strategies to reduce on this blood loss. Antifibrinolytics such as tranexemic acid have been successfully used to reduce perioperative blood loss in other orthopaedic procedures.

However effectiveness of tranexemic acid use during open femoral shaft fracture intramedullary nailing surgery has not been studied in our setting.

Aim: To assess the effectiveness of intravenous tranexemic acid in reduction of perioperative blood loss, transfusion rates in patients undergoing open femoral shaft fracture intramedullary nailing surgery.

Methods: This will be an open label single arm study. Patients scheduled for open femoral shaft fracture intramedullary nail fixation surgery will receive preoperative tranexemic acid at 15mg/kg. Blood loss using difference between pre and post-operative hemoglobin, blood transfusion rates and adverse events in the peri operative period will be measured.

Utility: The results of this study will reveal effectiveness of tranexemic acid in reducing perioperative blood loss during open femoral shaft fracture surgery in this setting. This information will be useful in designing protocols for prevention of perioperative blood loss for femoral shaft fracture surgery.

OPERATIONAL DEFINITIONS

Peri-operative

- Period from start of surgery to 72 hours after the Surgery

ORIF

- Open intramedullary nailing of femoral shaft fractures.

CHAPTER ONE

INTRODUCTION

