3.8.2 Outcome Variables

- . Primary Outcome: Perioperative blood loss –Will be represented as difference in the 2 hour pre-operative and 72 hour post-operative hemoglobin concentration in g/dl.
- . Secondary Outcome: Blood Transfusion – will be represented as the number of blood units. 450mls of whole blood will equate to 1 unit of whole blood. 200mls of packed cells will equate to 1 unit of whole blood.
- . Secondary Outcome: Safety – Will be described as adverse events secondary to administration of Tranexemic Acid observed in patients in the study during the perioperative period.
 - Anaphylaxis
 - Dizziness
 - Hypotension
 - Nausea and Vomiting
 - Diarrhoea
 - Thrombo -embolic Events
 - Others.....

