APPENDIX II: Data Collection Sheet

Study Number.....

Date of Surgery

Study Arm A
 B

A. Patient information

1) Inpatient number 2) Age (yrs)

3) Sex: M F 4) Weight (kg)

B. Pre-operative Data

1) Duration of Injury (Days) 2) Fracture Pattern (AO / OTA)

 A B C

3) Preoperative Hemoglobin (g/dl) 4) Platelet Count

5) aPTT 6) PT-INR

C. Procedure Data

1) Type of Anaesthesia 2) Time : Start of Surgery

GA Regional

3) Time : End of Surgery 4) Duration of Surgery (hrs)

5) Nailing Approach 6) Whole Blood Units Transfused

Ante grade / Retrograde

7) Adverse Event/s Y N (Describe Event/s)

D. Postoperative Data

1) Whole Blood Units Transfused 2) 72hr Post-operative Hemoglobin (g/dl)

3) aPTT

4) PT-INR

Peri-operative Blood Loss (g/dl)

$$= \text{Pre-opHb} - (\text{Post-opHb} + \text{Blood Units})$$

$$= \dots - (\dots + \dots)$$

$$= \dots \text{ (g/dl)}$$

Intraoperative and Post-operative Adverse Events and complications

Pre / Intraoperative Period				Comments
DVT / TEE	Nausea Vomiting Diarhoea	Anaphylaxis Dermatitis	Hypotension	
Others				
Day 1				Comments
DVT / TEE	Nausea Vomiting Diarhoea	Anaphylaxis Dermatitis	Hypotension	
Others				
Day 2				Comments
DVT / TEE	Nausea Vomiting Diarhoea	Anaphylaxis Dermatitis	Hypotension	

Others				
Day 3				Comments
DVT / TEE	Nausea Vomiting Diarhoea	Anaphylaxis Dermatitis	Hypotension Dizziness	
Others				
Day 3-14				Comments
DVT / TEE	Nausea Vomiting Diarhoea	Anaphylaxis Dermatitis	Hypotension Dizziness	
Others				

**APPENDIX III: Transfusion Guidelines for patient's participating in
“EFFECTIVENESS OF PREOPERATIVE INTRAVENOUS TRANEXEMIC
ACID ON REDUCTION OF PERIOPERATIVE BLOOD LOSS IN OPEN
INTRAMEDULLARY NAIL FIXATION OF FEMORAL SHAFT FRACTURES
IN MULAGO” Study**

Category 1	Circle	Transfusion Criteria
Intraoperative Hemoglobin Concentration of < 7g/dl	YES / NO	Transfuse with 1 Unit of WB or PRBC if 1 Criteria in category 1 is met
Category 2		
Intraoperative Hemoglobin Concentration of < 10g/dl	YES / NO	Transfuse with 1 Unit of WB or PRBC if 1 criteria in Category 2 is met together with 3 criteria in Category 3
Category 3		
Severe bleeding at the surgical site and soiling of surgical drapes and mops	YES / NO	Transfuse with 1 Unit of WB or PRBC if ≥ 4 criteria in Category 3 are met
Tachycardia	YES / NO	
Oxygen Saturation < 90%	YES / NO	
Hypotension	YES / NO	
Severe pallor of the Mucous Membranes	YES / NO	
Decreasing Levels of Consciousness	YES / NO	
Dyspnoea	YES / NO	
Angina	YES / NO	

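### The primary-outcome formula takes transfused units off the haemoglobin loss instead of adding them back, an error of 2 g/dl per unit, and other sections define the outcome differently

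*Combined protocol and SAP*

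**What the plan says.** Section 3.7.8 names the quantity to be measured: "Total blood loss due to the surgical procedure will be represented by total hemoglobin loss in the perioperative period". It then gives the formula "Total Blood Loss = Pre-opHb – (Post-opHb + Blood Units g/dl", with the bracket closing after the units. The Appendix II data sheet repeats the same arithmetic, with blanks for staff to fill in, under the label "Peri-operative Blood Loss (g/dl" (again a bracket that closes there).

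Section 3.7.6 supplies the conversion: "450mls of whole blood and 200mls of packed red blood cells will be estimated to be equivalent to 1g/dl rise in hemoglobin level".

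Other places give no transfusion term. Section 3.8.2 says of the primary outcome: "Will be represented as difference in the 2 hour pre-operative and 72 hour post-operative hemoglobin concentration in g/dl". The abstract, the primary objective in 1.6.2.1 and Objective 1 in 3.12 use equivalent wording.

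On counting units, 3.8.2 adds that "200mls of packed cells will equate to 1 unit of whole blood". The operational definitions fix the perioperative window as "Period from start of surgery to 72 hours after the Surgery". The postoperative block of the data sheet opens with "1) Whole Blood Units Transfused 2) 72hr Post-operative Hemoglobin (g/dl", and the sheet has a separate units field for the procedure itself.

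The benchmark, in 3.6.1, is a mean loss of 3.31 g/dl (SD 1.56) from an earlier series of 93 patients at the same hospital. The documents do not say whether or how that figure allowed for transfusion.

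**The concern.** A transfusion raises the 72-hour haemoglobin and so hides part of the loss. A formula for total loss has to undo that. The printed one moves the wrong way: with the same two haemoglobin values, a patient who needed more blood is recorded as having lost less. The separate plain-difference wording is a legitimate measure of haemoglobin fall, but it is not the total loss that 3.7.8 names, and the plan does not say which of the two enters the t-test in 3.12.

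This is the primary outcome of a single-arm study. There is no concurrent control group scored by the same rule, so an error in the outcome cancels only if the historical figure happens to share it. Section 3.7.6 ties transfusion to signs of bleeding, so the patients with the largest losses are likely to be distorted most.

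**Working it through.** **Inputs**
- Target quantity: total haemoglobin loss (3.7.8).
- One unit U raises haemoglobin by 1 g/dl (3.7.6).
- Benchmark 3.31 g/dl, SD 1.56, anticipated reduction 30% (3.6.1).
- Transfusion rates in the two trials reviewed in 2.3.3: 18/45 on placebo against 7/45 on the drug, and 30% against 5.6%.

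**The plan's own figure.** The target difference is 0.3 × 3.31 = 0.993 g/dl, and n = (1.96 + 0.84)² × 2 × 1.56² / 0.993² = 38.7, rounded to 39. This reproduces. The point does not depend on it, but n = 39, the SD and the 0.993 are used below.

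**Algebra.** For units given between the two samples:
- Post = Pre − Loss + U
- Correct: Loss = Pre − Post + U = Pre − (Post − U)
- Plain difference: Pre − Post = Loss − U
- Printed: Pre − (Post + U) = Loss − 2U

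| Pre | Post | Units | Loss | Plain difference | Printed formula |
|---|---|---|---|---|---|
| 12 | 9 | 0 | 3 | 3 | 3 |
| 12 | 9 | 1 | 4 | 3 | 2 |
| 12 | 9 | 2 | 5 | 3 | 1 |

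The printed value can go negative. With Pre 12, a true loss of 3.31 and 2 units, Post is 10.69 and the formula gives 12 − 12.69 = −0.69.

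**Effect on the comparison with 3.31.** This depends on how 3.31 was computed. The documents give no expected units per patient for this study, so what follows is illustration, with one unit per transfused patient.

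*Case A: 3.31 was correctly adjusted, and the drug does nothing.* A mean of 0.993/2 = 0.497 units per patient would produce the whole planned effect under the printed formula; the plain difference would need 0.993 units. The table shows simulated one-sample t-tests against 3.31 (n = 39, SD 1.56, lower tail 2.5%, 400,000 trials per cell). The false-significance columns assume transfusion independent of loss; brackets there give a latent correlation of 0.5.

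| Patients given one unit | Mean, printed (apparent reduction) | Mean, plain (apparent reduction) | False significance, printed | False significance, plain |
|---|---|---|---|---|
| 15% | 3.01 (9%) | 3.16 (4.5%) | 18% (23%) | 8% (9%) |
| 30% | 2.71 (18%) | 3.01 (9%) | 52% (69%) | 20% (24%) |
| 40% | 2.51 (24%) | 2.91 (12%) | 75% (91%) | 32% (39%) |

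The corrected formula gives 2.5% throughout. Section 3.12 could instead mean a test against 0.7 × 3.31 = 2.317. With a true mean of exactly 2.317 and transfusion rates like those on the drug in 2.3.3 (5.6% and 15%), false rejection is 6% and 18% (printed) or 4% and 8% (plain).

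*Case B: 3.31 carries the same error as the trial.* Where the drug lowers transfusion, benefit is understated. Printed: 2 × (0.30 − 0.056) = 0.488, or 2 × (18/45 − 7/45) = 0.489 g/dl, which is 49% of 0.993. Plain: 0.244 g/dl, or 25%.

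*Case C: 3.31 is a plain difference and only the trial is corrected.* Benefit is understated by the mean units per benchmark patient. At 0.30 to 0.40 units this is 0.30 to 0.40 g/dl, or 30% to 40% of 0.993.

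**The case against.** Several points can fairly be made for the plan.

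- **The plain difference is not an arithmetic error.** It is a valid haemoglobin fall, and it is what the entry for the primary outcome in 3.8.2 describes. This stands. For those passages the fault is that they conflict with 3.7.8, not that they are wrong in themselves. Reading 3.7.8 as the intended definition is an inference, though a reasonable one: it is the most detailed statement, and the data sheet follows it.
- **The large false-significance figures are conditional.** They need 3.31 to have been correctly adjusted, one unit per transfused patient, and assumed transfusion rates; the 15% row pairs no drug effect with a rate seen on the drug. This also stands. Under Case B the bias runs the other way, so the direction cannot be stated.
- **The timing of units is mostly settled.** The perioperative window ends at 72 hours, and packed cells already have a unit equivalence. What remains is small: the postoperative units field is not expressly limited to blood given before the 72-hour sample, while follow-up in 3.7.7 runs to 2 weeks.
- **The error is recoverable.** The sheet records both haemoglobin values and the units separately, so the right value can be computed at analysis. That limits the harm if the error is noticed, but the plan as written directs the wrong calculation.

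None of this rescues the printed sign. It appears in the main text and again on the data sheet, and nothing elsewhere corrects it.

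**Conclusion.** The concern holds and needs to be fixed. Given the plan's own conversion of 1 g/dl per unit, the formula in 3.7.8 and Appendix II understates total haemoglobin loss by exactly 2 g/dl per unit given between the samples. The plain difference used elsewhere understates it by 1 g/dl per unit. Untransfused patients are unaffected. A single unit shifts that patient's printed value by about twice the 0.993 g/dl the study is sized to detect.

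The per-unit errors need no outside figure. The effect on the study's conclusion does: its size depends on how much blood is given, and its direction on how 3.31 was computed, and the documents state neither. If 3.31 was correctly adjusted, both versions lean towards benefit. If it carries the same error, they understate benefit where the drug reduces transfusion. If it is a plain difference, correcting the trial alone would count against the drug.

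**What to change.** - In 3.7.8 and Appendix II, write: total blood loss (g/dl) = Pre-opHb − Post-opHb + units transfused between the two haemoglobin samples, in the whole-blood equivalents of 3.7.6 and 3.8.2.
- Make the abstract, 1.6.2.1, 3.8.2 and 3.12 refer to that single definition, so that it is clear what the primary test uses.
- Add a line to the data sheet saying that the units entered in the formula are those given before the 72-hour sample, with 200 ml of packed cells counted as one unit.
- Confirm from the benchmark source how 3.31 treated transfusion. If it was computed differently, put the trial and the benchmark on the same basis. If this cannot be confirmed, report the possible mismatch as a limitation.

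The cost is one sign in two places, aligned wording in four others, one line on the form and a check of one source. The stated sample size does not change, and no extra patients or blood samples are needed. The definition should be settled before outcome data are examined, so that it cannot be chosen in the light of the results.
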